## **F4 Statistical Methods**

This is a randomized smoking cessation trial. Simple  $\chi^2$  tests, logistic regression models and cox proportional hazard models will be used to study the association between genetic markers and cessation outcomes.

We will use generalized linear models with logit as the link function to model the primary outcome (7-day point prevalence abstinence at 12 weeks/end of treatment). We will construct

---

contrast models for each specific hypothesis testing and compare the goodness of fit for each contract. The primary method of analysis will be estimating a standard series of regression equations to test main effects, and gene – environment interaction (effect moderation).

Detailed analysis plan is included in the Statistical Analysis Plan (SAP) in Appendix K10.

## ***F5 Missing Outcome Data***

If a participant prematurely discontinues the study medication, the reason for discontinuation will be determined and classified as primarily due to an adverse event, or lack of efficacy, not wanting to take another medication, or others. We will examine missing data for causes and compare the groups with respect to side effects and efficacy. We will adhere to the intent-to-treat principle for smoking outcome analyses, so that dropouts will be treated as smoking. In addition, we will analyze the missing data under conditions of both missing completely at random (MCAR) and missing at random (MAR), and use appropriate strategies such as imputation when appropriate.

Participants who drop off the trial before they get a dose of the study medication/placebo will be included in the analyses of efficacy if they receive the medication packet. They will be included in the safety analyses if medication was dispensed to them. We will ensure an appropriate informed consent process to minimize the probability of drop out. We will also assess level of adherence to the study protocol and these information will be available for use in secondary analyses.

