### **3.b Treatment Regimen**

During the baseline visit (visit 1), all participants will be randomized at 1:1:1 to 1) one arm of combination nicotine and smoking cessation counseling, or 2) varenicline and smoking cessation counseling, and 3) another arm of placebo and smoking cessation counseling at no cost to participants. Participants will receive enough patches to last 12 weeks. The duration of medication treatment is 12 weeks (standard for participants who smoke >9 cigs/day=8 weeks of 21mg, 2 weeks of 14mg, and 2 weeks of 7mg nicotine patches; standard for participants who smoke 5-9 cigs/day=8 weeks of 14mg and 4 weeks of 7mg;).

**Nicotine Lozenge:** The 4 mg dosage is recommended for patients who take their first cigarette within 30 minutes of waking and the 2mg dosage is recommended for patients who take their first cigarette more than 30 minutes after waking. Participants will begin taking lozenges a week before abstinence to replace some cigarettes. Participants will then take 1 lozenge every 1-2 hours for 6 weeks, then 1 lozenge every 2-4 hours for 3 weeks, and 1 lozenge for every 4-8 hours for 3 weeks. Participants will be encouraged to take a minimum of 4 pieces/day unless this amount produces adverse effects.

**Varenicline:** Varenicline will be initiated with a titration for 7 days before the quit date. Before the quit date, participants will take one 0.5mg tablet daily for 3 days, then two 0.5mg tablets for 4 days (one in the morning and one in the evening). After the quit date (day 8), participants will take 1mg tablet in the morning and in the evening.

**Placebo:** 50% of participants assigned to the placebo group will receive placebo patch/lozenge, and 50% will receive the placebo pill as a control for the two active medication arms.

All participants will be given complete instructions on proper medication use, and will be urged to contact his/her physician and a study hotline number immediately in case of listed symptoms of nicotine toxicity or side effects. Dose changes or discontinuation of NRT may be recommended; all changes will be addressed in analyses of adherence outcomes.

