### **3.g Packaging**

The study medication (Nicotine patch and place patch, varencliline, and placebo (patch and lozenge or pill) will have identical packaging when they are provided to the participants.

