### **3.i Receiving, Storage, Dispensing and Return**

Participants will receive their study medication when they attend the in office visit 1 (baseline).

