## **F Statistical Plan**

### ***F1 Sample Size Determination and Power***

We will recruit 822 subjects for this study to examine whether genotypes predict the efficacy and side effects of cessation medications. The sample size is based on the statistical power calculation based on current research findings. Based on published finding of effect size (OR=3.1), we will have power of 0.84 to detect a hypothesized interaction effect size of 2.0 with the study design (2 sided  $\alpha=0.05$ , abstinence rate 20% in the placebo group).

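### F5 promises intent-to-treat, but read literally its inclusion rule gives a modified intent-to-treat efficacy set conditioned on receiving the medication packet; the likely effect is small

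*Combined protocol and SAP*

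**What the plan says.** Section F5 contains two rules on who counts for efficacy. The first is general: "We will adhere to the intent-to-treat principle for smoking outcome analyses, so that dropouts will be treated as smoking". The second, in the following paragraph, covers people who leave before a first dose. They "will be included in the analyses of efficacy if they receive the medication packet". The safety rule comes next: "They will be included in the safety analyses if medication was dispensed to them". The efficacy and safety conditions therefore rest on what is in effect the same event.

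On timing, section 3.b states: "During the baseline visit (visit 1), all participants will be randomized at 1:1:1". Section 3.i places the hand-over of study medication at that same visit.

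On form, the cNRT arm receives patch and lozenge and the varenicline arm receives tablets. For placebo, section 3.b says "50% of participants assigned to the placebo group will receive placebo patch/lozenge, and 50% will receive the placebo pill". Section 3.g says that the study medications "will have identical packaging when they are provided to the participants".

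No section of the supplied text says that all randomised participants are analysed for efficacy. F3 and F4 refer to a detailed plan in Appendix K10, which appears in the supplied text only as a heading.

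**The concern.** Someone who is randomised and then leaves without the packet is a dropout. Under the first F5 rule that person is counted as smoking. Under the second, the condition for entering the efficacy set is not met. An analyst cannot follow both rules for such a person, and the literal reading of the second is a modified intent-to-treat set under an intent-to-treat label.

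The condition comes after allocation, so the exclusion need not be balanced. No participant takes both forms: varenicline is all pill, cNRT is all patch and lozenge, and pooled placebo is half of each. If some people decline because of the form they are offered, one active arm loses about twice the share that pooled placebo loses, and the other active arm loses none. Since the people left out would mostly be scored as smoking, leaving them out raises the abstinence rate in whichever arm loses more.

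**Working it through.** The plan gives no figure for non-receipt of the packet, so there is nothing of its own to reproduce here. The power figure in F1 does not bear on this point.

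**Inputs from the documents.** F1: "We will recruit 822 subjects for this study", and 20% abstinence on placebo. Section 3.b: 1:1:1 allocation, so 822/3 = 274 per arm, with the placebo arm split evenly by form (137 pill, 137 patch/lozenge). F1 also gives the hypothesised interaction odds ratio of 2.0.

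**Assumptions.** A share k of people allocated pills decline the packet (k = 3%, 5%, 10%) and nobody declines patches. Abstinence among packet recipients is 40% on varenicline and 20% on placebo. Every decliner is counted as smoking, which is the extreme case.

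**Number left out.** People allocated pills: 274 + 137 = 411. Left out: 411k = 12.3, 20.6, 41.1, or about 12, 21 and 41.

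**Varenicline main effect.** With the exclusion, OR = (0.40/0.60)/(0.20/0.80) = 2.67 for every k. Counting all randomised, the varenicline arm loses k and the pooled placebo arm k/2:

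OR = odds(0.40(1−k)) / odds(0.20(1−k/2))

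| k | varenicline rate | placebo rate | OR, all randomised | OR, packet set |
|---|---|---|---|---|
| 3% | 0.388 | 0.197 | 0.634/0.2453 = 2.58 | 2.67 |
| 5% | 0.380 | 0.195 | 0.613/0.2422 = 2.53 | 2.67 |
| 10% | 0.360 | 0.190 | 0.5625/0.2346 = 2.40 | 2.67 |

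**If there is no true effect.** Let both arms have 20% abstinence counting all randomised, with the active arm losing d and placebo d/2. The packet-based odds ratio is odds(0.20/(1−d)) / odds(0.20/(1−d/2)), which is 1.01, 1.03 and 1.07 for d = 2%, 5% and 10%.

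**The other active arm.** Under the same pill-only refusal, cNRT loses nobody and placebo loses k/2, so the shift runs the other way. With 40% also assumed on cNRT, counting all randomised gives 0.6667/0.2453 = 2.72, 0.6667/0.2422 = 2.75 and 0.6667/0.2346 = 2.84, against 2.67 in the packet set.

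**Primary hypotheses.** Both are genotype × medication interactions. Take refusal as unrelated to genotype and a 20% placebo rate in each genotype group. The placebo odds then cancel, and the interaction OR counting all randomised is odds(a₁(1−k)) / odds(a₀(1−k)), where a₁ and a₀ are the recipients' abstinence rates on varenicline in the risk and reference genotypes.

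- Medication OR 1 in the reference genotype: a₀ = 0.20 and a₁ = 1/3 (odds 0.25 × 2 = 0.5). Results: 0.4778/0.2407 = 1.985; 0.4634/0.2346 = 1.976; 0.4286/0.2195 = 1.952.
- Medication OR 2 in the reference genotype: a₀ = 1/3 and a₁ = 1/2 (odds 0.5 × 2 = 1). Results: 0.9417/0.4778 = 1.97; 0.9048/0.4634 = 1.95; 0.8182/0.4286 = 1.91.

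In both settings the packet-based value is 2.0.

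**The case against.** The strongest reply is that the exclusion is inferred. The sentence is worded as an inclusion rule and may have been meant to keep undosed people in. Nothing says outright that randomised people without a packet are dropped, and K10 may define the efficacy set. This stands as a limit on how firmly the point can be put. It does not remove the point, because the sentence attaches a condition and nothing in the supplied text overrides it.

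The window is also narrow. A loss needs someone to seek treatment, consent after hearing the medication risks, pass the allergy exclusions, be randomised, and leave the same visit empty-handed. That stands, and the number could be zero.

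The unbalanced mechanism is possible but not shown. Packaging is stated to be identical, and coded assignment means that refusal within a form should not track active versus placebo. The form could be known at hand-over, since E3 provides an instruction sheet at visit 1 and the K9 attachment covers patch and pill use, but the documents do not say that it is known before receipt. F3 also compares the two placebo forms before pooling them.

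A reader might infer that the rule removes precisely the people who would be scored as failures. The documents do not support that: section 2.h provides for collecting smoking status from consenting people who stop treatment, so someone who declined could still be assessed. Nor do they support the inference that the trial's comparisons cease to rest on randomisation, given how few people could be involved.

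**Conclusion.** F5 is wrong as written in a limited sense: the intent-to-treat property it claims is not what its inclusion rule delivers when read literally. The rule gives a modified intent-to-treat set conditioned on a post-randomisation event.

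The severity is minor. Under pill-only refusal of 3% to 10%, the varenicline main-effect odds ratio is 2.67 with the exclusion and 2.58 to 2.40 without it. The refusal rates, the 40% abstinence and the scoring of every decliner as smoking are assumptions; the documents give no refusal rate.

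A reader might go on to infer that the primary tests are compromised. They are not, on these figures: an interaction odds ratio of 2.0 becomes about 1.95 to 1.99, or 1.91 to 1.97 if medication already has an odds ratio of 2 in the reference genotype. This assumes that refusal is unrelated to genotype. The documents state no such link, and section 2.d keeps genotype coded and withheld from staff. What is exposed is mainly the medication main effects, which F3 and Aim 2 also set out to test.

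**What to change.** Replace the F5 sentence on efficacy inclusion with: *All randomised participants are included in the efficacy analyses in the arm assigned, whether or not they received or took medication; those without a verified outcome are counted as smoking.* Keep the packet-based set as a sensitivity analysis labelled modified intent-to-treat. If K10 defines the efficacy set, bring the two texts into line.

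The cost is one sentence, with no new data, visits or participants. Estimates may become slightly less favourable for an arm whose participants decline the packet more often. If nobody leaves without a packet, the results are unchanged.

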### **C3 Rationale for the Selection of Outcome Measures**

We will conduct a randomized controlled smoking cessation trial of 822 participants to examine the association between the genetic variants (CHRNA5), treatment, and cessation success (abstinence at end of treatment (ABST\_EOT)). We will evaluate secondary cessation outcomes (abstinence at 6 months and 1 year).

**Primary Outcome Measure:** 7-day point prevalence abstinence [Time Frame: Week 12]  
The definition of this measure requires: (a) no self-reported smoking (not even a puff of a cigarette) for at least the 7 days prior to the assessment, and (b) CO biochemical verification of abstinence.

**Secondary Outcome Measures:** Continuous Abstinence (11 weeks) [Time Frame: 12 weeks with the first 1 week initial grace period]

The definition of this measure requires: Not taking even 1 cigarette puff from target quit date to end of treatment with the first 1 week initial grace period.

**7-day point prevalence quit rate** [Time Frame: Week 24]

The definition of this measure requires: (a) no self-reported smoking (not even a puff of a cigarette) for at least the 7 days prior to the assessment, and (b) biochemical verification of abstinence.

Number of days to lapse and relapse [Time Frame: Assessed from the target quit day through 52 weeks.]

The number of days to lapse is defined as the number of days from the target quit date until the participant reports smoking (even a single puff). The number of days to relapse is defined as the number of days from the target quit day until the first of seven consecutive days of smoking.

Initial Cessation [Time Frame: Assessed for the first seven days after the target quit date.]  
Defined as at least 1 day of abstinence during the first 7 days after the target quit day.

Longitudinal models of abstinence outcomes across multiple time points [ Time Frame: 0-52 Weeks ]

The definition of this measure requires; no self-reported smoking (not even a puff of a cigarette) for at least 7 days prior to the assessment.

Longitudinal models of smoking quantity in cigarettes per day outcomes across multiple time points. [ Time Frame: 0-52 Weeks ]The definition of this measure requires self-reported cigarettes per day.

Medication adherence [ Time Frame: Pre-quit week to Week 12 ]Adherence is the proportion of expected medication (varenicline, patch, lozenge) taken as advised during pre-quit week to week 12

Side effects [ Time Frame: Pre-quit week to Week 12 ]

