All reported side effects (occurring>4%) will be summarized and presented for the study. In addition, the investigators will further identify a pre-specified set of key side effects as being related to drug agonist effects (e.g., nausea, vomiting, racing heart, headache, and sleep disturbance). These will be analyzed as rate of occurrence during the period of medication use.

Withdrawal [ Time Frame: Pre-quit week to Week 4 ]

Withdrawal severity is assessed by Wisconsin Smoking Withdrawal Scale (WSWS) overall withdrawal scores, craving, and negative affect scores.

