#### **4.g Adverse Event Reporting Period**

Adverse events will be recorded and reported throughout the entire duration of this study follow up period of 1 year for each participant.

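### F5 defines the safety set by dispensing rather than by a first dose, so per-person side-effect proportions are diluted by the never-dosed share

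*Combined protocol and SAP*

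**What the plan says.** Section F5 (Missing Outcome Data) sets both analysis populations for people who leave before treatment starts. For efficacy: "Participants who drop off the trial before they get a dose of the study medication/placebo will be included in the analyses of efficacy", provided that they were given the medication packet. For safety, the next sentence reads: "They will be included in the safety analyses if medication was dispensed to them". Neither population requires a dose.

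Section D3, 3.i fixes when dispensing happens: "Participants will receive their study medication when they attend the in office visit 1 (baseline"). Sections 3.b and 3.d place randomisation at the same visit.

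Section C3 describes two side-effect summaries, with an outcome time frame from the pre-quit week to Week 12. The general one is: "All reported side effects (occurring>4%) will be summarized and presented for the study". The second covers a pre-specified set of key agonist-type effects: "These will be analyzed as rate of occurrence during the period of medication use". C3 does not say for either summary whether the denominator is persons or person-time.

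Medication use is self-reported at each follow-up visit in the three-month treatment period (3.e, and the schedule in E2).

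**The concern.** Being given a packet is not exposure. F5 itself foresees people who are given medication and leave before using any. Keeping them is a sound choice for efficacy: randomisation is preserved, and dropouts count as smoking. For safety it works the other way. These people enlarge the denominator and cannot have a drug-related event, so the reported proportions fall below those among people who were treated.

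Side effects are a listed secondary outcome, and F1 gives the study's purpose as examining whether genotype predicts side effects as well as efficacy. At stake are the accuracy of the reported risks, which effects pass the 4% screen, and the absolute differences between arms.

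**Working it through.** The documents give no never-dosed share and no expected side-effect rate, so there is no figure of the plan's own to reproduce. Everything below except N and the allocation is an assumption, shown over a range.

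**Inputs**
- N = 822 (F1), allocated 1:1:1 (2.d), so 822 / 3 = 274 per arm.
- Safety set = dispensed (F5), with dispensing at Visit 1 (3.i).
- f = share of dispensed participants who never take a dose. Assumed 2%, 5%, 10% or 20%.
- People who leave before a dose report no side effects. This is exact for events counted during medication use. It is an assumption for the general summary, which is not limited to time on medication.

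**1. Dilution of a proportion**

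Reported proportion = true proportion among the dosed × (1 − f). True rate needed to reach 4% = 4% / (1 − f).

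| f | dosed per arm, 274 × (1 − f) | a true 20% reads | true rate needed to reach 4% |
|---|---|---|---|
| 2% | 268.5 | 19.6% | 4.08% |
| 5% | 260.3 | 19.0% | 4.21% |
| 10% | 246.6 | 18.0% | 4.44% |
| 20% | 219.2 | 16.0% | 5.00% |

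The last column applies only if the screen is taken over the F5 safety set.

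**2. Comparison of arms, equal f**

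Take true risks of 30% and 10% with f = 10% in both arms. The reported risks are 27% and 9%. The difference falls from 20 to 18 points, and the ratio stays at 27 / 9 = 3.0.

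**3. Comparison of arms, unequal f**

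Take the same true 20% in both arms, with f = 15% in one and 5% in the other. The reported risks are 0.20 × 0.85 = 17% and 0.20 × 0.95 = 19%. The ratio is 17 / 19 = 0.895 where the truth is 1.

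**4. Power**

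The formula is the normal approximation for two proportions, two-sided 5%: Φ[(d − 1.96 × SE0) / SE1], with SE0 pooled and SE1 unpooled.
- 20% vs 10%, 274 dosed per arm (no never-dosed): 0.908.
- 18% vs 9%, 274 per arm (dispensed set, f = 10%): 0.871.
- 20% vs 10%, 247 per arm (dosed set, f = 10%): SE0 = √(2 × 0.15 × 0.85 / 247) = 0.0321, SE1 = √(0.25 / 247) = 0.0318, power 0.878.

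Nearly all of the loss from 0.908 occurs because undosed people carry no information about the drug. The choice of safety set moves power only from 0.871 to 0.878. The issue is the size of the estimates, not the ability to detect a difference.

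**The case against.** **The rate may be per person-time.** If the C3 rate for key side effects is events per time on medication, never-dosed people add nothing to numerator or denominator, and there is no dilution. This stands for the key set. It does not cover per-person proportions, and a screen at 4% reads most naturally as one.

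**The size is unknown and may be small.** At f = 2%, a 20% risk reads 19.6%. This stands.

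**The dispensed set is explicit and avoids exclusions based on missing self-report.** People who leave early may never say whether they dosed, and counting them as exposed returns some of them to the denominator. This stands in part. If f = 10% and use is unknown for half of those people, a true 20% reads 20% × 0.90 / 0.95 = 18.9%, against 18.0% under the present rule. The fix removes only those known not to have dosed.

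**The detailed SAP (K10) may define denominators.** Only its heading is in the supplied text, so this cannot be checked. The F5 rule is stated all the same.

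**A stronger reading.** A reader might infer from the on-medication window that arms with earlier stopping will look safer. The documents do not support this, for four reasons.
- It needs the rate to be a per-person proportion. Assume a constant hazard giving 20% over 13 weeks: λ = −ln(0.8) / 13 = 0.01716 per week. If a share s stops at week 4, the proportion is (1 − s) × 0.200 + s × 0.0664. That gives 17.3% at s = 20% and 14.7% at s = 40%. Per person-time the rate stays at 1.716 per 100 person-weeks.
- It can reverse. If 16 of the 20 points fall in the first two weeks, the person-time rate rises from 1.843 to 2.062 and 2.362 per 100 person-weeks as s goes from 0 to 20% and 40%.
- It needs stopping to be unrelated to the event. An event that prompts stopping occurs on medication and is counted, so that person is already in the numerator for that effect.
- The window covers only the key set. Section 2.h collects adverse effects after treatment withdrawal where consent is given, and 4.g states: "Adverse events will be recorded and reported throughout the entire duration of this study follow up period of 1 year for each participant". Section 4.c stops at end of treatment, so the collection period itself needs reconciling.

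**Conclusion.** The point holds as a defect in the definition of the safety set. F5 knowingly keeps people with no exposure in the safety denominator, and any per-person proportion over that set is too low by the factor (1 − f). For a true 20% the shortfall is 0.4 points at f = 2%, 1 point at 5%, 2 points at 10% and 4 points at 20%. Absolute differences shrink in the same proportion. Ratios are distorted only if f differs between arms.

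This rests on assumed values of f, on person-based denominators, and on never-dosed people reporting no events. If some of them do report symptoms in the general summary, the dilution there is smaller. Nothing in the documents shows that f is large or unequal. The change is worth making because the rule is explicit, it errs in the non-conservative direction for safety, and the data needed to correct it are already collected.

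**What to change.** **F5.** Define the safety set as participants who took at least one dose of study medication or placebo, based on the self-reported use already collected. Count participants with unknown use as exposed. Keep the dispensed set as a sensitivity analysis. Leave the efficacy population as it is.

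**C3.** State the denominator of each side-effect summary, including the 4% screen. Report key side effects per person-time on medication, and beside it the proportion of dosed participants with an event from first dose through Week 12. The second summary should stand alongside the on-medication rate and not replace it: counting through Week 12 regardless of stopping takes in time off drug, so neither summary is complete alone.

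**Cost.** A few sentences and one extra table. The safety denominator becomes slightly smaller, reported rates become slightly higher, and membership of the set depends on self-reported use.
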